The target of our study is to have 100 subjects complete the study, excluding prior pilot study data. We will run a blinded interim analysis on the primary endpoint when 25 subjects in each arm have completed treatment and follow-up, and a conditional power for detecting a significant treatment effect by the planned end of the study (100 subjects) will be determined. If this conditional power is between 50 and 80%, the sample size will be recalculated to achieve 80% conditional power following the algorithm of Chen and DeMets (2004). Otherwise, the study will continue until 100 patients have completed treatment.

Based on prior pilot study data, we anticipate the study dropout rate to be approximately 30%, from time of initial enrollment to completion of the post-treatment survey. During the prior pilot study, the dropout rate was 50% initially, and dropped to 30% during the last 8 months of enrollment, until the study was closed. Dropout rate was the same in each arm, with 5 subjects in each arm dropping out after starting treatment. Only three subjects cited adverse events (AEs) as a reason for drop out; two subjects on placebo complained of headache and dry mouth, respectively, and one subject on amitriptyline complained of sedation.

Thus, we anticipate a dropout rate during treatment of 30%, and anticipate having to enroll at least 75 subjects in order for 25 patients in each arm to complete the study by the interim analysis.

The physician may elect to discontinue study drug due to serious adverse events (SAEs) or unintended pregnancy. If a subject withdraws from treatment due to adverse events, we will ask that they continue coming in for follow-up visits and finish the remaining parts of the visits off the study drug.

The primary endpoint of the trial will be the total modified RSI at 8 weeks. The Reflux Symptom Index (RSI) has been validated by Belfasky et. al. [Belafsky PC, Postma GN, Koufman JA. Validity and reliability of the reflux symptom index (RSI). *Journal of Voice*. 2002;16:274-277]. The RSI is a questionnaire consisting of 9 statements to be ranked 0-5. We have added two additional symptoms to be assessed with the RSI, "throat pain or burning" and "pain with swallowing", which we believe are also relevant to chronic laryngeal neuropathy.

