The total modified RSI score at 8 weeks will be averaged for each group (amitriptyline vs. placebo) and differences compared between the treatment and placebo arms using analysis of covariance adjusting for baseline severity scale at an overall two-sided 0.05 level of significance across the interim and final analysis (a two-sided significance level

of 0.00306 at the interim and 0.049 at the final analysis). A Wilcoxon Rank Sum test will be used in the case that the data is found to have a non-normal distribution.

A secondary outcome will be improvement in overall symptoms (yes/no), as subjectively assessed by patients. The post treatment survey will ask both the patient and the principal investigator whether they thought the subject was on amitriptyline or placebo.

Additional secondary outcomes will be whether there are changes in scores from baseline on the Voice Handicap Index-10 after treatment [Rosen et. al. Development and Validation of the Voice Handicap Index-10. *The Laryngoscope*. 2004; 114: 1549-1556] and change in score from baseline on the Cough Severity Index (CSI).[Shembel AC et al.. Development and validation of the cough severity index: a severity index for chronic cough related to the upper airway. *Laryngoscope*. 2013;123(8):1931-6.] The VHI-10 is a 10-question scale that addresses effects on quality of life from voice disorders while the CSI is a 10-item likert scale that assesses cough symptoms. Furthermore, we will determine whether the severity of each symptom within the modified RSI has improved after treatment. This will account for questions that may be less relevant to laryngitis overall (and more specific to reflux).

Frequencies of AEs for both groups of patients and the rate of discontinuing treatment will be recorded.

The study will be stopped if any patient is permanently disabled, seriously injured, or dies in a manner that could be consistent with the drug usage. The study will be continued if said patient(s) were taking the placebo or the event is demonstrably unrelated to the subject's participation in the trial.

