An independent monitor within the otolaryngology department who is not associated with study recruitment or data analysis will also review adverse events for all subjects. The independent monitor will submit a report to the PI, who will then review these events and submit a report to the IRB. Also, if there is a concerning event or group of events, the PI will bring these to the attention of the independent monitor as they occur.

A report will be submitted to the IRB and the PI by the independent monitor at the intervals described in safety monitoring section (see section on Safety monitoring/reporting for more detail).

Analysis (efficacy and safety)

We will be using the 8 week post-treatment 11-point modified RSI score as our primary outcome. Treatments will be compared using analysis of covariance adjusting for the baseline value using a two-sided 0.05 level of significance.

We thus used the RSI to calculate our sample size. The average starting RSI for subjects with a similar type of laryngitis to what we are studying is 20.9. After treatment, the average was 12.8 (Belfasky et. al. 2002). We estimated a 20% improvement for the

placebo group, using the estimate for continuous indicators from Hróbjartsson et. al. meta-analysis of placebo effects. Thus, we predicted the final mean RSI for the placebo patients to be 16.72. The difference between the means is thus assumed to be 3.92. Dividing this mean difference by the anticipated standard deviation (10.0, using the value from Belfasky et. al. for the final RSI value post-treatment) gives an anticipated standardized effect size of 0.392. Using this for the calculation for a-priori sample size calculations (using two-sided $p < 0.05$ and a desired power level of 0.8) gives a needed sample size of 208.

In prior pilot study data, mean difference in RSI scores was +13 (increase in score post treatment) for the amitriptyline group and +16.4 in the placebo group, with standard deviations of 7.8 and 12.1, respectively. The p-value used to determine significance was 0.5 for a two-tailed unpaired t-test.

Currently, funding is available for 100 subjects to complete this study, not including subjects who completed treatment in the prior pilot study. With a dropout rate of 30%, we expect to enroll 130 subjects in order for 100 to complete treatment. With a standard deviation of 10 as per prior assumptions, we would be able to detect a mean difference of 6 by one-tailed ANOVA analysis.

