When 25 subjects in each arm (placebo and amitriptyline) have completed the study and follow-up (i.e. at least 50 subjects total), a blinded interim analysis will be performed, and conditional power for detecting a significant treatment effect by the planned end of the study (100 subjects) will be determined. If this conditional power is between 50 and 80%, the sample size will be recalculated to achieve 80% conditional power following the algorithm of Chen and DeMets (2004). Otherwise, the study will continue until 50 subjects in each arm have completed treatment.

For data analysis, we will be performing both per-protocol and multiple imputation approach analyses. Multiple imputation using the linear regression approach will be used to impute missing data, for subjects who do not complete treatment. Intention-to-treat analysis is not possible, since our outcomes are determined by the 8 week post-treatment survey, and there are no intermediate data points with regards to treatment efficacy outcomes (ie, subjects who drop out will not have any outcomes recorded).

The primary outcome measure will be the pre- and post- treatment difference in scores on the Reflux Symptom Index (RSI), with two additional questions added to assess for symptoms that may be more specific to chronic laryngeal neuropathy.

The RSI is a validated questionnaire consisting of 9 statements to be ranked 0-5. We have added two additional symptoms to be assessed to the RSI, "throat pain or burning" and "pain with swallowing", which we believe may also be relevant to chronic laryngeal neuropathy.

The modified RSI score will be averaged for each group (amitriptyline vs. placebo), and since it is a nearly continuous variable (with an expected normal distribution) and we will

be comparing the mean of the change rather than categorizing the treatment into responder and non-responders, we will also analyze it using an Analysis of Covariance or Wilcoxon Rank Sum test if determined to have a non-normal distribution.

For the modified RSI, we will also conduct a secondary analysis looking at change in severity of each symptom individually. This will account for questions that may be less relevant to laryngitis overall (and more specific to reflux).

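### The primary outcome is defined in two ways and the Wilcoxon fallback drops the baseline adjustment without saying when it applies or what it ranks; name one outcome and fix baseline-adjusted ANCOVA as the only primary test

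*Combined protocol and SAP*

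**What the plan says.** Study Design gives one definition: "The primary endpoint of the trial will be the total modified RSI at 8 weeks". It describes the comparison in the same terms: "The total modified RSI score at 8 weeks will be averaged for each group (amitriptyline vs. placebo) and differences compared", by ANCOVA adjusted for baseline severity. The opening of Analysis (efficacy and safety) agrees: "We will be using the 8 week post-treatment 11-point modified RSI score as our primary outcome".

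Later in the same Analysis section the definition changes: "The primary outcome measure will be the pre- and post- treatment difference in scores on the Reflux Symptom Index (RSI", with the two added items. The text there says that the mean change is what will be compared.

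Both sections provide a fallback. In Study Design it reads: "A Wilcoxon Rank Sum test will be used in the case that the data is found to have a non-normal distribution". The Analysis section repeats the choice between ANCOVA and Wilcoxon directly after the wording about change, and states that normality is expected. Neither section names a normality test or threshold, describes a baseline adjustment for the Wilcoxon, or says plainly whether it ranks the total or the change.

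The same endpoint feeds the interim rule: "If this conditional power is between 50 and 80%, the sample size will be recalculated to achieve 80% conditional power".

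**The concern.** A confirmatory analysis should be reproducible from the plan alone. Here at least three readings of the fallback are open:

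- **Total reading:** check the 8-week total and, if it is non-normal, rank the total.
- **Change reading:** check the change and, if it is non-normal, rank the change.
- **Mixed reading:** check the total but rank the change. The later Analysis text allows this, because its grammatical subject is the score while its stated comparison is of changes.

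These can give different answers to whether the trial is positive. When the total is ranked, the information in the baseline score is also discarded, although both sections otherwise call for adjustment. That matters in a trial funded for 100 completers when its own calculation asks for 208. The conditional power at the interim also has no defined test behind it.

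**Working it through.** **1. The plan's own figure.** Placebo mean 20.9 × 0.8 = 16.72 ("Thus, we predicted the final mean RSI for the placebo patients to be 16.72"); treated mean 12.8; difference 3.92; SD 10; standardized effect 0.392. The normal formula gives n per arm = 2(1.960 + 0.842)²/0.392² = 102.2, so 103 per arm and 206 in total. The t-test version gives 103.13, so 104 per arm and 208 in total, as stated. The levels 0.00306 and 0.049 combine to 0.0500 overall at half the information, also as stated.

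**2. The two definitions under ANCOVA.** If Y = a + τ·T + b·B + e, with T treatment and B baseline, then Y − B = a + τ·T + (b − 1)·B + e. The treatment effect τ, its standard error and its p-value are unchanged. In simulated trials the two p-values differed by at most about 4 × 10⁻¹⁴. The conflict therefore has no effect while ANCOVA is used. It acts only through the fallback.

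**3. Is the fallback a realistic event?** "The RSI is a questionnaire consisting of 9 statements to be ranked 0-5"; with two more items the total runs from 0 to 11 × 5 = 55. Normal scores with the plan's figures would put Φ(−16.72/10) = 4.7% of placebo and Φ(−12.8/10) = 10.0% of amitriptyline scores below 0, where none can lie. Scores piling up at the floor can trip a normality check.

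These means and the SD come from the 9-item RSI. If only the means are scaled by 11/9 (placebo 20.44; amitriptyline 20.44 − 3.92 = 16.52), the shares fall to Φ(−2.044) = 2.0% and Φ(−1.652) = 4.9%. With the plan's means and SD 7.8 they are Φ(−2.144) = 1.6% and Φ(−1.641) = 5.0%. The value 7.8 is the pilot SD of change in the amitriptyline arm, used here only as a sensitivity value.

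**4. Simulation.** From the documents: 50 per arm, two-sided 0.049, difference 3.92, and the means and SD above. Assumed, because the documents do not give them: Shapiro-Wilk at 0.05 on pooled scores, baseline SD equal to the 8-week SD, baseline correlation 0.3 to 0.7, and scores rounded and limited to 0–55. The main run used 6,000 trials per setting (Monte Carlo error about 0.6 points for power). The ranges also cover smaller repeat runs.

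| Scores | Check of total fires | Total and change readings disagree | Power of total reading against ANCOVA | Total and mixed readings disagree |
|---|---|---|---|---|
| Plan's means, SD 10 | 78–80% | 10–29% | −3 to −23 points | 24–33% |
| Means × 11/9 only, or SD 7.8 | 17–19% | 3–7% | −1 to −6 points | 5–7% |
| Right-skewed (gamma) | not summarised | 19–30% | about +6 at correlation 0.3, −17 at 0.7 | not summarised |

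Detail for the first row, at correlation 0.3/0.5/0.7: fixed ANCOVA has power 50.5/59.8/75.1% and the total reading 47.2/50.4/52.6%, a loss of 3.3/9.4/22.5 points. The change reading has 49.6/58.9/74.2%, because a check of the change fires in only 5–7% of trials. Scaling means, SD and difference together by 11/9 brings back the first row almost unchanged (fires in 76–78%, disagreement 10/16/26%).

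**5. Type I error.** Any one rule fixed in advance gave 4.3–5.3%.

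**6. Ranking or lost adjustment?** Rank ANCOVA with baseline, in the first-row case, has power of about 49/57/72%, against 45/48/45% for an unadjusted Wilcoxon on the total. With skewed scores the figures are 63/71/83% against 60/59/57%. Ranking costs little; dropping the baseline costs more as the correlation rises.

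**The case against.** - **The sections can be read as checking the same variable.** In Study Design the fallback follows a sentence about the total, and in the Analysis section the subject of the sentence is also the score. This is a fair reading, and it weakens the claim that the checked variable is wholly open. It does not settle what the Wilcoxon ranks, and it leads to the mixed reading, which disagrees with the total reading at least about as often as the change reading does.
- **The large figures depend on one input.** This stands. Putting 9-item means with SD 10 on a 0–55 scale produces the 78–80% firing rate, and modest changes cut it to 17–19%. Only the full range is a fair summary.
- **A rank test helps when scores are skewed.** This stands in part. At correlation 0.3 the total reading gains about 6 points over ANCOVA; at 0.7 it loses about 17. The sign turns on a correlation that the documents do not give.
- **Inflated type I error.** A reader might infer that the ambiguity raises the false-positive rate to about 10%. The documents do not support that. A figure of 8.7–10.4% arises only if ANCOVA or either Wilcoxon may be reported regardless of the normality check, which the plan does not allow. Choosing the better of the total and change readings afterwards gives 5.3–6.3% with bounded normal scores and 7.0–7.9% with skewed ones.
- **Effect on the interim decision.** A reader might also want a figure for how often the 50–80% decision would change. That needs a definition of conditional power, such as the observed trend, which the documents do not state. No size is claimed here.

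**Conclusion.** The point holds. The plan contradicts itself on the primary outcome, and its fallback has no stated trigger and no baseline adjustment. Those findings come from the text and carry high confidence.

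The sizes carry less. They depend on the assumed correlation, normality test, score distribution and carry-over from 9 to 11 items. Disagreement between the total and change readings runs from about 3% to about 30% of trials, and the power cost of the total reading from about 1 to 23 points when scores are near-normal.

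It would be wrong to conclude that the two definitions by themselves change the result, since ANCOVA treats them identically. The case rests on reproducibility and on the lost adjustment, not on error inflation. The plan should be corrected before unblinding; either outcome could be defended, but the plan has to choose one.

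**What to change.** 1. In Study Design and throughout Analysis (efficacy and safety), state that the primary outcome is the 8-week total of the 11-item modified RSI. Correct the later Analysis wording that refers to the pre-to-post difference and to the mean change.
2. Delete the normality-triggered Wilcoxon test from both sections.
3. Make ANCOVA, with treatment and baseline total modified RSI as terms, the single primary test at both the interim and the final analysis.
4. Report rank ANCOVA with the same baseline term as a sensitivity analysis that cannot replace the primary test. Say whether it uses completers or imputed data.

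The cost is wording only: no new data, visits or patients. ANCOVA also pools directly over the multiple imputations already planned. The price is power if scores prove strongly right-skewed: 52.0/59.7/73.7% for ANCOVA against 61.9/70.4/83.2% for rank ANCOVA at correlation 0.3/0.5/0.7, or about 9–11 points.

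### Does the 6-point detectable difference for 100 completers fail because it is tied to a one-tailed ANOVA while the primary test is two-sided?

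*Combined protocol and SAP*

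**What the plan says.** Under Analysis (efficacy and safety), the combined protocol and SAP sets the primary comparison: "Treatments will be compared using analysis of covariance adjusting for the baseline value using a two-sided 0.05 level of significance". Study Design divides that level between the two looks, with two-sided levels "of 0.00306 at the interim and 0.049 at the final analysis".

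The sample-size paragraph in the same Analysis section takes the treatment effect from published values: "The difference between the means is thus assumed to be 3.92". With a standard deviation of 10, two-sided p < 0.05 "and a desired power level of 0.8) gives a needed sample size of 208".

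The section then turns to the budget: "Currently, funding is available for 100 subjects to complete this study", pilot subjects not counted. The disputed sentence closes that paragraph. "With a standard deviation of 10 as per prior assumptions", it says, "we would be able to detect a mean difference of 6 by one-tailed ANOVA analysis". It gives neither a significance level nor a power. Later in the section, the default end of the trial is stated per arm: unless the interim rule changes the size, "the study will continue until 50 subjects in each arm have completed treatment".

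**The concern.** A detectable difference means something only for a given test, level and power. Here the test named is one-tailed, the power is missing, and the planned primary test is two-sided. A one-sided test at the same nominal level needs a smaller difference to reach the same power. A reader could therefore suspect that the funded trial was made to look more sensitive than it is.

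This is also the only sentence that says what 100 completers can show, and it follows a two-sided calculation calling for 208. If the 6 held only for a one-sided test, the plan would overstate its sensitivity at the size it expects to reach. Sidedness matters for the assumed effect too: with 100 completers, 3.92 points has about 62% power on a one-sided 0.05 test and about 49% on a two-sided 0.049 test, both unadjusted.

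**Working it through.** **Inputs.** From Analysis (efficacy and safety): standard deviation 10, 100 completers (50 per arm), stated detectable difference 6, assumed difference 3.92, and two-sided 0.05 with power 0.8 for the 208. From Study Design: two-sided 0.049 at the final analysis. The correlation between baseline and 8-week score is not given, so it is assumed and varied below.

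**The plan's 208 first.** Per arm, n = 2 × [(1.960 + 0.842) / 0.392]² = 102.2, so 103 per arm and 206 in total by the normal approximation. The noncentral t gives 104 per arm, 208 in total, with power 0.803. The figure reproduces as a two-sided calculation.

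**Detectable difference at 50 per arm.** The standard error of the difference is 10 × √(2/50) = 2.0. The detectable difference is 2.0 × (z for the level + z for the power):

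- one-sided 0.05, 80% power: 2.0 × (1.645 + 0.842) = 4.97
- two-sided 0.05, 80% power: 2.0 × (1.960 + 0.842) = 5.60
- two-sided 0.049, 80% power: 2.0 × (1.968 + 0.842) = 5.62

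The noncentral t on 98 degrees of freedom gives slightly larger values:

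| Test | 80% power | 90% power | Power for 6 points |
|---|---|---|---|
| One-sided 0.05 | 5.01 | 5.89 | 90.9% |
| Two-sided 0.05 (same as F test) | 5.66 | 6.55 | 84.4% |
| Two-sided 0.049 | 5.68 | 6.57 | 84.2% |

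**Which reading fits the 6?** One-sided at the section's own power of 0.8 gives 5.0, which does not round to 6. Two-sided at 0.8 gives 5.66, which does. One-sided at 90% gives 5.89, and two-sided at 85% gives 5.99 by the normal approximation, but neither 85% nor 90% appears anywhere in the documents. The figure cannot be tied to one calculation with certainty. The reading that uses only stated quantities is the two-sided one.

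**Why one-tailed ANOVA can mean the two-sided test.** An ANOVA F test rejects only for large F. With two arms F = t², so its upper tail holds both tails of t. For 6 points the F noncentrality is 100 × (0.5 × 6/10)² = 9, which is (6/2.0)², and the power is 84.4%, the same as the two-sided t-test at 0.05.

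**Effect of the baseline covariate.** With residual standard deviation 10 × √(1 − r²), 97 degrees of freedom and two-sided 0.049:

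| Assumed r | 80%-power difference | Power for 6 | Power for 3.92 |
|---|---|---|---|
| 0 | 5.68 | 84% | 49% |
| 0.3 | 5.42 | 87% | 53% |
| 0.5 | 4.92 | 93% | 61% |
| 0.7 | 4.05 | 99% | 77% |

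Adjustment can only help here, so leaving it out makes the 6 more cautious.

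**Fewer completers.** If 130 are enrolled and 30% drop out, 130 × 0.7 = 91 complete. By the normal approximation at two-sided 0.049, the 80%-power difference is then 5.89 and power for 6 is 81%. Enrolment is a separate matter, but the 6 survives it.

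**The case for a change.** The strongest case for a change is that readers should not have to infer the test. Taken literally, one-tailed contradicts a plan that is two-sided everywhere else, no power is attached, and the final level of 0.049 is not used. The 6 fits both a two-sided 80% reading rounded up and a one-sided 90% reading, which carry different error rates. Rewriting one sentence would settle it and could add the power for 3.92 points.

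Part of this stands: the adjective is ambiguous, and the power has to be carried over from two paragraphs earlier. The rest does not lead to a change. Because the intended reading is unsettled, it cannot be stated as fact that the sentence describes a test the trial will not use. Moving from 0.05 to 0.049 shifts the detectable difference by only 0.02 (5.66 to 5.68).

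A power for 3.92 would be additional information and would correct nothing printed: the section already shows 3.92 assumed, 208 needed and 100 funded. A lone 49% would also give only the least favourable end of the range for the planned covariance analysis. Finally, the standard deviation of 10 comes from the published 9-item index, while the endpoint has 11 items, so replacing 6 with 5.7 would offer little real precision.

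**Conclusion.** The concern does not call for a change. The sentence is loosely worded, but its number is sound. At a standard deviation of 10 and 50 completers per arm, 6 points has about 84% power on the planned two-sided level and about 91% if one-tailed is taken literally, so it is detectable with more than 80% power either way. Against the 80%-power difference of 5.68, the stated 6 is cautious by about 0.3 points before baseline adjustment.

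No decision rests on the adjective. The 100 comes from funding, the primary test is fixed as two-sided in both Study Design and Analysis (efficacy and safety), and any increase in size depends on conditional power at the interim. An analyst following the plan would run the two-sided test whatever this sentence says.

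The conclusion assumes that the standard deviation of 10 carries over to the modified index and that about 50 per arm complete. It does not depend on the unknown baseline correlation, since any correlation raises the power.

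### No planned analysis tests whether dropout is related to the missing week-8 score; a 6-point result would withstand most plausible departures, a 5-point result would not

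*Combined protocol and SAP*

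**What the plan says.** Under Analysis (efficacy and safety), the combined protocol and SAP states: "For data analysis, we will be performing both per-protocol and multiple imputation approach analyses". Imputation is by linear regression for subjects who do not complete treatment. No predictors are listed. The same paragraph rules out intention-to-treat because efficacy is measured only at week 8, so no outcome is expected from anyone who leaves.

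Under Study Design, the expected loss is given as "we anticipate a dropout rate during treatment of 30"%. The pilot lost 50% at first and 30% later, with five subjects leaving each arm after starting treatment. Three pilot subjects gave adverse events as the reason, two on placebo and one on amitriptyline. The same section says that subjects who withdraw for adverse events will be asked to keep attending visits off drug.

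The primary test is ANCOVA on baseline, at an "overall two-sided 0.05 level of significance across the interim and final analysis", with levels "of 0.00306 at the interim and 0.049 at the final analysis". No shifted, reference-based or tipping-point analysis appears anywhere.

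**The concern.** The two planned analyses look like a check on each other, but with respect to dropout they share one assumption. Omitting leavers treats completers as representative. Regression imputation with arm and baseline gives an amitriptyline leaver the score of an amitriptyline completer with a similar baseline. Agreement between the two would therefore say little about subjects who left because the drug did not help or was not tolerated. Better predictors would sharpen the imputation without testing the assumption. With no intermediate efficacy scores, the data cannot test it either.

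The pilot's equal dropout counts do not settle the matter: equal numbers leaving do not show equal outcomes among those who left. At stake is how far a positive result can be trusted when nearly a third of the scores are modelled.

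**Working it through.** **Inputs from the plan.** SD 10 ("Dividing this mean difference by the anticipated standard deviation (10.0"); 50 completers per arm; 30% dropout; final two-sided level 0.049; a difference of 6, which the plan calls detectable with 100 completers.

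**1. The plan's own sample size.** "The difference between the means is thus assumed to be 3.92": 20.9 × 0.80 = 16.72 on placebo, less 12.8 on treatment, is 3.92. With SD 10 ("using two-sided $p < 0.05$ and a desired power level of 0.8"), the normal approximation gives 206 in total and the t-based calculation gives 208, as stated.

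**2. Result among completers.** SE = 10 × √(2/50) = 2.00. The critical difference at 0.049 is about 3.99. A difference of 6 gives t = 3.0, p about 0.003.

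**3. Tipping point, simple form.** Let d be the missing fraction and δ the extra points by which amitriptyline dropouts alone score worse than imputed. Estimate = D − d × δ, so the tipping point is (D − 3.99)/d.
- D = 6: (6 − 3.99)/0.30 = 6.7
- D = 5: (5 − 3.99)/0.30 = 3.4
- D = 4.5: (4.5 − 3.99)/0.30 = 1.7

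**4. The same by multiple imputation with Rubin's rules** (50 observed and about 22 missing per arm). For D = 6 the tipping point is about 6.4. A penalty of 6 gives p about 0.04, and 6.7 gives p about 0.055. Because 6.4 to 6.7 exceeds 6, amitriptyline dropouts would have to finish slightly worse than placebo subjects.

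**5. Specific departures** (same inputs, no baseline correlation).

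| Departure | D | Estimate | p |
|---|---|---|---|
| Amitriptyline dropouts imputed from placebo model | 6 | 4.2 | about 0.03 |
| Same | 5 | 3.5 | about 0.07 |
| Amitriptyline dropouts lose 3.92 points | 6 | 4.8 | about 0.02 |
| Both arms' dropouts return to baseline (8.1 and 4.18 points) | 6 | 4.8 | about 0.02 |
| Equal shift of 6.7 in both arms | 6 | 6.0 | about 0.004 |

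In the first row the p-value is a little below that for a flat penalty of 6, because both arms' imputations then share the placebo model and the SE is smaller.

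**6. How the D = 6 threshold moves.**
- 130 enrolled, as planned for 100 completers: d = 15/65 = 23.1%, threshold 8.3 to 9.0. (The plan quotes 30% loss beside 130, but 100/0.70 = 143, so both fractions are shown.)
- Baseline correlation, an assumption since none is given, at 30% missing: 7.0 to 7.5 for r = 0.3; 8.1 to 8.6 for r = 0.5 (SE = 10 × √0.75 × √(2/50) = 1.73); 9.8 to 10.6 for r = 0.7.
- 50% dropout, the pilot's first rate: (6 − 3.99)/0.50, about 4.0.

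**7. If arm were left out of the imputation model**, dropouts in both arms would be drawn to the pooled mean and a difference of 6 would shrink to 6 × 0.70 = 4.2. That would be a by-product of the model, not a planned test.

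**The case against.** The strongest case on the other side is that a 6-point result is not fragile under the departures one would think of first. It survives placebo-like dropouts, loss of the drug-specific effect, return to baseline in both arms and an equal shift in both arms. It fails only if amitriptyline leavers, and they alone, end up worse than placebo subjects. The pilot gives no support for a penalty in the drug arm only. All of this stands.

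A reader might infer more: that because the treated arm is assumed to go from 20.9 to 12.8 ("After treatment, the average was 12.8"), a gain of 8.1 points, amitriptyline dropouts who merely lose their benefit would overturn a 6-point result. A penalty of 8.1 does give an estimate of about 3.5 and p of 0.08 to 0.09. But the plan credits placebo with 4.18 of those points, so only 3.92 is attributable to the drug. Removing all 8.1 from amitriptyline dropouts while placebo dropouts keep 4.18 is a one-sided scenario that the documents do not support. With 130 enrolled, an 8.1-point penalty leaves p at about 0.046, still below 0.049.

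Continued visits after withdrawal for adverse events could also reduce the missing fraction. That helps only for that group, and the analysis section expects no outcomes from dropouts. None of these points supplies the missing analysis; they only move the threshold.

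**Conclusion.** The gap is real and worth closing, but it is not a fatal flaw. With arm in the imputation model, neither planned analysis departs from the assumption that leaving is unrelated to the unseen score given the predictors.

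Its size depends on the result obtained. A completer difference of 6 tips at about 6.4 to 6.7 points in amitriptyline dropouts only, with a range from about 4 (50% dropout) to about 8 to 9 (130 enrolled, or r = 0.5). A difference of 5 tips at about 3.4 and fails placebo-based imputation. Smaller positive results matter here: the planning difference of 3.92 lies just under the unadjusted critical value of 3.99, so a positive trial could sit close to the boundary.

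These figures rest on SD 10, 50 completers per arm, two-sided 0.049 and, except where stated, 30% missing and no precision gain from baseline. Actual dropout and correlation will be known only at the end, which is why the tipping point should be a required part of the report.

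**What to change.** In Analysis (efficacy and safety):

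1. State that the imputation model includes arm and baseline modified RSI, and list any other predictors.
2. Pre-specify a sensitivity analysis on the same imputed data sets. Add a penalty to the imputed week-8 modified RSI of amitriptyline dropouts in 1-point steps from 0 to at least 8, repeat the primary ANCOVA at each step, and report the tipping point beside the primary result.
3. Add one run that imputes amitriptyline dropouts from the placebo arm's model.
4. Reconcile the Study Design text on continued visits after withdrawal for adverse events with the statement that dropouts have no outcomes, and say that any week-8 score collected after withdrawal will be used.

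The cost is a short SAP paragraph, fixed before unblinding, and a few extra runs. No new visits or subjects are needed. The downside is that a positive result may have to be described as fragile; equally, a result that holds can be reported with more confidence.
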